6.1 Study treatment

6.1.1 Investigational and control drugs

Investigational and control drugs are summarized in Table 6-1 (no limitation to the list).

Patients will receive ACEI/ARB, where generics are acceptable and listed in Table 6-1. Patients will initiate ARNI treatment after a 36-hr washout period after the ACEI treatment. Basically, initiated ARNI dosage accord to ACEI/ARB alternative dosage, but investigators have discretion to prescribe ARNI dosage.

Table 6-1 Investigational and control drug

(Name) Dosage Form Administration (local)	Drug (Name)	Pharmaceutical Dosage Form	Route of Administration	Supply Type	Sponsor (local)
---	----------------	-------------------------------	----------------------------	-------------	--------------------

Drug (Name)	Pharmaceutical Dosage Form	Route of Administration	Supply Type	Sponsor (local)
Sacubitril/Valsartan, 50mg	Tablet	Oral use	Oral use Open label subject packs;	
Control Drug				
ACEI				
Enalapril	Tablet	Oral use	Open label subject packs;	No supply
Captopril, 6.25 mg, 50 mg	Tablet	Oral use	Open label subject packs;	No supply
Perindopril, 2 mg, 8 mg	Tablet	Oral use	Open label subject packs;	No supply
Ramipril, 1.25 mg, 10 mg	Tablet	Oral use	Open label subject packs;	No supply
Benazepril, 2.5 mg, 20 mg	Tablet	Oral use	Open label subject packs;	No supply
ARB				
Candesartan, 4 mg, 32 mg	Tablet	Oral use	Open label subject packs;	No supply
Valsartan, 40 mg, 160 mg	Capsule	Oral use	Open label subject packs;	No supply
Losartan, 25 mg, 150 mg	Tablet	Oral use	Open label subject packs;	No supply

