6.1.5 Treatment duration

The planned duration of treatment for ACEI/ARB and ARNI is 6 months each. During the ACEI/ARB period, the drug choice and dosage are at the discretion of the physician. The EOS will occur when the pre-specified number of patients completed the 12 months treatment. Patients may be discontinued earlier due to unacceptable toxicity and/or treatment is discontinued at the discretion of the investigator or the patient. For patients who in the opinion of the investigator are still deriving clinical benefit from ARNI, every effort will be made to continue provision of study treatment.

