3.3.1 Dose escalation guidelines

The dosage of ACEI/ARB and ARNI are under Investigator's discretion according to the recommended dosage (Yancy et al 2017) (Table 3-1). The recommended starting dose of ARNI for different population is presented in Table 3-2. If the patient is well tolerated, the dose of study drug should be up-titrated to next dose level until to target dose. Down-titration of the study drug at any time based on the judgment of the Investigator will be allowed with the consideration for patient safety and tolerability.

Compound	Initial dose	Target dosage
ARNI (Sacubitril/Valsartan)	50 – 100 mg bid	200 mg bid
ACEI		
Enalapril	2.50 mg bid	10 mg bid
Captopril	6.25 mg tid	50 mg tid
Perindopril	2.00 mg qd	8 mg qd
Ramipril	1.25 mg qd	10 mg qd
Benazepril	2.5 mg qd	20 mg qd
ARB		
Candesartan	4 mg qd	32 mg qd
Valsartan	40 mg bid	160 mg bid
Losartan	25 – 50 mg qd	150 mg qd

Table 3-1 Recommended dosage

Table 3-2 Recommended	starting dose of ARNI
1 abic 5-2 itecommended	

Population	Initial dose
Moderate or high-dose ACEI (equivalent of enalapril ≥ 10 mg bid)	100 mg bid
Moderate or high-dose ARB (equivalent of valsartan ≥ 80 mg bid)	100 mg bid
Low dose ACEI (equivalent of enalapril < 10 mg bid)	50 mg bid
Low dose ARB (equivalent of valsartan < 80 mg bid)	50 mg bid
Severe renal impairment (eGFR < 30 mL/min/1.73 m ²)	50 mg bid
Moderate hepatic impairment (Child-Pugh Class B)	50 mg bid
Elderly (age \geq 75 years)	50 mg bid

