4.2 Safety Endpoints

4.2.1 Duration of exposure and exposure dose

In this study, detailed information such as date, time, dose and frequency of administration will be recorded in the CRF. The extent of exposure to ACEI/ARB and ARNI will be investigated, and the duration of exposure and planned and actual doses will be calculated.

Duration of exposure (days) = date of the last dose of the IMP - date of the first dose of the IMP + 1 If the subject's duration of drug exposure is discontinuous, the number of days without drug use will not be counted.

Total planned dose (mg) = total planned daily dose recorded in CRF * duration of exposure (days). Total actual dose (mg) = total actual daily dose recorded in CRF * duration of exposure (days).

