4.4 Past and concomitant medication and concurrent treatment

The CRF collects the drug name, total daily dose and unit, frequency of administration, route of administration, start date, end date, ongoing or not, and indication for prior and concomitant medications.

The CRF collects the name, start date, end date, ongoing or not, and indication of concomitant treatments (non-drug concomitant treatments, including surgery).

4.5 **Protocol Deviation and Medication Compliance**

Protocol deviations will be recorded by the clinical monitor.

Medication compliance for ACEI/ARB and ARNI is defined as: total actual dose/total planned dose *100%. Overall medication compliance for ACEI/ARB and ARNI will be summarized.

5. Statistical Hypotheses

For details, see section 7.4 Efficacy Analysis.

6. Analysis Datasets

The analysis data sets of this study are as follows.

Screened set

It includes all subjects who have signed the informed consent form.

Safety Analysis Set, SS

It includes all subjects who had received at least one dose of study treatment. Analyses will be performed according to the study treatment received. The safety analysis set will be used for all analyses except the efficacy analysis.

Efficacy Analysis Set

It includes SS subjects who have received ARNI at least once and completed 12 months of complete treatment and follow-up or who have early withdrawn from the study after receiving ARNI at least once. The efficacy analysis set will be used as the primary population to analyze the efficacy variables.

Per Protocol Set, PPS

It includes subjects in efficacy analysis set who had no major protocol violations, and the PP population will be used for efficacy analysis.

7. Statistical Methods

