7.2.2 Derived and converted data

Except for the calculation of certain study endpoints based on the data collected from CRF, no other data are derived or converted. For outliers, data queries are reported to the DM and solved or verified before database lock. No special data processing is performed.

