7.5 Safety Analysis

7.5.1 Drug exposure

The analysis is performed based on the SS.

The exposure to the study drug (duration of exposure, total planned dose, total actual dose) will be statistically described and summarized by treatment group and by mean, standard deviation, median, minimum, and maximum.

The number and percentage of patients in each treatment group will be summarized for duration of exposure in the following groups.

- < 30 days
- 30 days <= duration of exposure <60 days
- 60 days <= duration of exposure <90 days
- 90 days <= duration of exposure <120 days
- 120 days <= duration of exposure <150 days
- 150 days <= duration of exposure <180 days
- Duration of exposure >=180 days

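### Pooled ACEI/ARB exposure in raw milligrams tracks which drugs were chosen rather than how far they were titrated (SAP 4.2.1 and 7.5.1)

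*SAP*

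**What the plan says.** SAP 4.2.1 gives two parallel definitions, "Total planned dose (mg) = total planned daily dose recorded in CRF * duration of exposure (days" and "Total actual dose (mg) = total actual daily dose recorded in CRF * duration of exposure (days". Neither is scaled to the drug taken.

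SAP 7.5.1 sets the reporting level: "The exposure to the study drug (duration of exposure, total planned dose, total actual dose) will be statistically described and summarized by treatment group", using mean, SD, median, minimum and maximum. The treatment groups are ACEI/ARB and ARNI. SAP 7.2.2 adds no dose equivalent: "Except for the calculation of certain study endpoints based on the data collected from CRF, no other data are derived or converted".

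The comparator is a mixture by design. SAP Table 3-1 (the same as Protocol Table 6-2) names five ACE inhibitors and three ARBs, each with its own initial and target dose. Protocol 6.1.1 leaves the list open ("Investigational and control drugs are summarized in Table 6-1 (no limitation to the list"), and Protocol 6.1.5 leaves the choice free: "During the ACEI/ARB period, the drug choice and dosage are at the discretion of the physician".

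The plan does have a titration aim. SAP 3.3.1 says: "If the patient is well tolerated, the dose of study drug should be up-titrated to next dose level until to target dose". Protocol sections 3 and 6.5 frame the aim as the target or the maximum tolerated dose. The only other dose-based measure in the SAP text is in SAP 4.5: "Medication compliance for ACEI/ARB and ARNI is defined as: total actual dose/total planned dose *100" (a percentage).

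**The concern.** A milligram of perindopril and a milligram of valsartan are not the same amount of treatment. SAP Table 3-2 recognises this by classing prior therapy in enalapril or valsartan equivalents: the same dose band begins at 20 mg a day for one and 160 mg a day for the other. An average of raw milligrams over a mixed group is driven by the share of patients on high-milligram drugs.

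The study is open-label and single-sequence, with ACEI/ARB always first. A reader who sees fewer arrhythmias in the ARNI period will ask how intensively the comparator was dosed. The planned ACEI/ARB milligram summary cannot answer that and may point the wrong way.

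**Working it through.** The documents state no figure for this point, so there is none to reproduce. The inputs are the doses in SAP Table 3-1 and the formula in SAP 4.2.1. The one added assumption is 180 days of exposure for a six-month period.

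**Step 1. Target daily dose = listed target dose × doses per day. Total = daily target × 180.**

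| Drug | Target per day (mg) | Total over 180 days at target (mg) | Lowest listed initial dose as % of target |
|---|---|---|---|
| Perindopril | 8 | 1,440 | 25 |
| Ramipril | 10 | 1,800 | 12.5 |
| Enalapril | 10 × 2 = 20 | 3,600 | 25 |
| Benazepril | 20 | 3,600 | 12.5 |
| Candesartan | 32 | 5,760 | 12.5 |
| Captopril | 50 × 3 = 150 | 27,000 | 12.5 |
| Losartan | 150 | 27,000 | 16.7 |
| Valsartan | 160 × 2 = 320 | 57,600 | 25 |

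Spread over the eight drugs: 320/8 = 40-fold. Within ACE inhibitors it is 150/8 = 18.75-fold; within ARBs it is 320/32 = 10-fold. Splitting the group by class would therefore not cure the problem.

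**Step 2. Order reversal between two patients.** Valsartan kept at its initial dose: 40 × 2 = 80 mg a day, or 80/320 = 25% of target; total 80 × 180 = 14,400 mg. Perindopril at target: 8 × 180 = 1,440 mg. The patient at 25% of target shows ten times the exposure of the patient at 100%.

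**Step 3. Order reversal between two groups (assumed mixes).**
- 80% enalapril and 20% valsartan, all at target: (0.8 × 20 + 0.2 × 320) × 180 = 80 × 180 = 14,400 mg.
- 20% enalapril and 80% valsartan, all at half target: (0.2 × 10 + 0.8 × 160) × 180 = 130 × 180 = 23,400 mg.

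The group at half the intensity has the larger mean.

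**Step 4. Does compliance fill the gap?** Both totals in SAP 4.2.1 use the same duration, so the days cancel and compliance is actual daily dose over planned daily dose. If planned means prescribed, a patient prescribed and taking the initial valsartan dose scores (80 × 180)/(80 × 180) = 100%. Compliance then says nothing about the dose level reached. The SAP does not define planned dose, so this step is conditional.

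**Step 5. The same data on a normalised scale.** As a percentage of each drug's own target, every drug at target reads 100%, so the 40-fold spread disappears. The two patients in step 2 read 25% and 100%, in the right order.

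**The case against.** **The table was never given this job.** Dose totals sit under safety endpoints and are reported on the safety set; nothing in the SAP says they are meant to show titration. That is fair, and it makes this a reporting weakness and not an error in the efficacy analysis. It does not rescue the pooled figure, which is no better as a description of exposure for safety.

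**The estimand does not depend on it.** A reader might infer that the ARNI comparison can be interpreted only if ACEI/ARB was fully titrated. The documents do not support that. Protocol 2.1 handles dose changes of either treatment by treatment policy and aims to mirror clinical practice, and titration is to tolerance as well as to target. Dose intensity helps to explain a difference; it does not decide whether the estimand is meaningful.

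**Other outputs may exist.** A reader might also infer that no planned output shows the dose reached. That cannot be known: SAP section 9 places table and listing templates in separate documents, which could break exposure down by drug. What stands is that the SAP text does not require it.

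**There are partial safeguards.** Protocol 9.1.1 ties treatment discontinuation to ACEI/ARB dosage staying below the guided level for one month, SAP 7.3.2 lists major deviations, and efficacy is repeated in the per-protocol set. The SAP does not say whether low comparator dosage counts as a major deviation, so these do not replace a dose summary.

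**Percentage of target is imperfect.** A patient at 25% of target may be at the maximum tolerated dose. This stands, and the report should say so.

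**Conclusion.** The point holds as a flaw in a planned descriptive summary. The pooled ACEI/ARB milligram totals reflect drug mix and can reverse the order of dose intensity. The 40-fold figure is exact for the eight named drugs at target, but the list is open, so it does not bound other drugs. The actual distortion is unknown because the documents give no drug mix: it is nil if every patient takes the same drug and grows as drugs with unlike milligram scales are mixed. The totals assume 180 days; the ratios do not. The compliance argument assumes that planned dose means prescribed dose.

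The McNemar tests, the hypotheses and the sample size do not use these totals. Nor do the documents show that the comparator was or will be under-dosed; the finding is only that this summary could not tell. ARNI milligram totals are sound within that group, because it contains one drug.

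**What to change.** In SAP 4.2.1 and 7.5.1, replace the pooled ACEI/ARB milligram totals with dose as a percentage of the patient's own drug's target daily dose in Table 3-1. For both periods, report:

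- the time-averaged percentage of target;
- the percentage at the end of the period (Visit 4 for ACEI/ARB, Visit 7 for ARNI);
- the number of patients at target.

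Keep milligram totals only by individual drug and for ARNI. List drugs outside Table 3-1 separately. Define planned dose. State with the table that a value below 100% may be the maximum tolerated dose and is not by itself evidence of under-dosing.

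Avoid a cut-off at 50% of target, because it cuts across Table 3-2: half of the enalapril target (5 mg bid) falls in the low class, whereas half of the valsartan target (80 mg bid) falls in the moderate-or-high class. If a categorical summary is wanted, use the Table 3-2 classes. Equivalents for the other six drugs would then have to be stated, since the documents do not give them.

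The cost is SAP wording and one derived variable, with SAP 7.2.2 amended to allow it. SAP 4.2.1 and Protocol 6.8.3 already have dose and dose changes recorded, so no new data collection is needed. The remaining limitation is that unlisted drugs have no reference target. The change concerns reporting only and alters no dosing rule.

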4.2.2 Adverse Events

Adverse Events

An adverse event (AE) is any untoward medical occurrence (e.g., any unfavorable and unintended sign [including abnormal laboratory findings], symptom or disease) in a clinical investigation participant after providing written informed consent for participation in the study. Therefore, an AE may or may not be temporally or causally associated with the use of a medicinal (investigational) product. Abnormal laboratory values or test results constitute AEs only if they fulfill at least one of the following criteria:

- they induce clinical symptoms or signs;
- they are considered clinically significant
- they require therapy

Treatment Emergent Adverse Event

A treatment emergent adverse event (TEAE) is an adverse event that occurs from the first dose of the study drug to 30 days after the last study treatment, or events occurring before the start of the treatment period and meeting any of the following three changes, as determined by the same preferred term (PT) under the same system organ class (SOC) based on MedDRA coding.

- (1) Events which are present prior to the start of the treatment period but increased in severity;
- (2) Events that change from being not suspected to being suspected of study drug relationship;
- (3) Events that develop into SAEs after the start of the treatment period.

The increase in severity described above means that the same PT under the same SOC is present before the first administration of the investigational drug, but the severity of the PT during treatment is higher than the most severe grade before administration, or a new adverse event that occurs during treatment has a more severe grade (the same PT under the same SOC).

Severity is graded as mild, moderate and severe:

- Mild: usually transient in nature and generally not interfering with normal activities.
- Moderate: sufficiently discomforting to interfere with normal activities.
- Severe: prevents normal activities.

Treatment emergent adverse events will be counted for the specific treatment period. TEAEs in the ACEI/ARB treatment group refers to the adverse events that occur after the subject's

first ACEI/ARB administration and before ARNI administration. If the subject has not taken ARNI, TEAEs in the ACEI/ARB treatment group refer to adverse events that occur from the subject's first ACEI/ARB administration to 30 days after the subject's last ACEI/ARB administration. TEAEs in the ARNI treatment group refer to adverse events that occur from the subject's first ARNI administration to 30 days after the subject's last ARNI administration.

Pre-treatment events

Pre-treatment adverse events are defined as those that occur after the signing of the informed consent form and before the day of first administration of the investigational drug.

Drug-related adverse events (adverse reactions)

An adverse drug reaction (ADR) is a toxic and adverse reaction to a drug. An ADR indicates that there is at least a reasonable likelihood of a causality between the drug and an adverse event. In this study, the causality between an adverse event and the investigational drug is judged according to "suspected" and "not suspected". "Suspected" adverse events are judged as adverse reactions. If the event is due to lack of efficacy or progression of underlying illness (i.e. progression of the study indication), the assessment of causality will usually be 'Not suspected.'

AEs leading to death

Adverse events leading to death will be recorded by the investigator on the CRF Adverse Events Form. In addition, there is a specialized CRF to record deaths.

Serious adverse events

SAEs will be collected between time patient signs ICF until 30 days after the patient has discontinued or stopped study treatment. An SAE is defined as any adverse event [appearance of (or worsening of any pre-existing)] undesirable sign(s), symptom(s), or medical conditions(s) which meets any one of the following criteria:

- fatal
- life-threatening

Life-threatening in the context of an SAE refers to a reaction in which the patient is at risk of death at the time of the reaction; it does not refer to a reaction that hypothetically might have caused death if it is more severe.

- results in persistent or significant disability/incapacity
- constitutes a congenital anomaly or birth defect
- requires inpatient hospitalization or prolongation of existing hospitalization, unless hospitalization is for:
 - routine treatment or monitoring of the studied indication, not associated with any deterioration in condition.

- elective or pre-planned treatment for a pre-existing condition that is unrelated to the indication under study and has not worsened since signing the informed consent.
- social reasons and respite care in the absence of any deterioration in the patient's general condition.
- treatment on an emergency outpatient basis for an event not fulfilling any of the definitions of an SAE given above and not resulting in hospital admission.
- is medically significant, e.g. defined as an event that jeopardizes the participant or may require medical or surgical intervention to prevent one of the outcomes listed above.

Medical and scientific judgment should be exercised in deciding whether other situations should be considered serious reactions, such as important medical events that might not be immediately life threatening or result in death or hospitalization but might jeopardize the patient or might require intervention to prevent one of the other outcomes listed above. Such events should be considered as "medically significant". Examples of such medical events are: allergic bronchospasm that requires intensive treatment in the emergency room or at home, blood dyscrasias or convulsions that did not lead to hospitalization or development of dependency or abuse.

Any suspected transmission via a medicinal product of an infectious agent is also considered a serious adverse reaction.

All reports of intentional misuse and abuse of the product are also considered SAE irrespective if a clinical event has occurred. Serious adverse events will be determined by the investigator on the original document or certified copy and entered into the CRF.

Adverse events leading to permanent discontinuation

In the study, action taken with study drug is drug discontinued or the subject will be withdrawn from treatment in response to these AEs.

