12.5.3 Safety endpoints

For all safety analyses, the SAF will be used and there will be no formal statistical inference analysis. All listings and tables will be presented by treatment group.

Safety summaries (tables and figures) include only data from the on-treatment period with the exception of baseline data which will also be summarized where appropriate (e.g. change from baseline summaries). In addition, a separate summary for death including on treatment and post treatment deaths will be provided. In particular, summary tables for AEs will summarize only on-treatment events, with a start date during the on-treatment period (treatment-emergent AEs).

Adverse events

All information obtained on AE will be displayed by treatment group and patient.

The number (and percentage) of patients with treatment-emergent AE (events started after the first dose of study medication or events present prior to start of double-blind treatment but increased in severity based on preferred term) will be summarized by treatment, primary system organ class, preferred term and maximum severity.

Separate summaries will be provided for study medication related AE, death, SAE, other significant AE leading to discontinuation and AE leading to dose adjustment.

The number and proportion of patients with AE as described in Section 10.1 will be summarized by treatment.

A patient with multiple AE within a primary system organ class is only counted once toward the total of the primary system organ class.

Adverse events which will be counted for a specific treatment period are those which are treatment-emergent. These events are those with an onset after the start of the treatment period, or which were present prior to the start of the treatment period but increased in severity, changed from being not suspected to being suspected of study drug relationship, or developed into SAEs after the start of the treatment period.

Vital signs

All vital signs data (see Section 8.4.2) will be listed by treatment group, patient, and visit/time and if ranges are available, abnormalities (and relevant orthostatic changes) will be flagged. Summary statistics will be provided by treatment and visit/time.

Clinical laboratory evaluations

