7.5.2 Adverse events

The analysis is performed based on the SS. The safety summary only analyzes data during

treatment.

The overall occurrence of adverse events during treatment will be summarized by treatment group, and the overall incidence of adverse events during various treatment periods will be calculated. The number and percentage (%) of subjects (n) with treatment emergent adverse events, treatment emergent serious adverse events, drug-related treatment emergent adverse events, treatment emergent adverse events leading to withdrawal from treatment, and treatment emergent adverse events leading to death will be summarized. A separate summary of deaths will also be provided, including the number of deaths during and after treatment. Upon calculating the frequency and percentage of subjects that experienced adverse events, if a subject developed multiple adverse events in the same classification, it would be counted once.

Among treatment emergent adverse events, the number (n) and percentage (%) of subjects with various adverse events by system organ class (SOC) and preferred term (PT) thereunder will be calculated by each treatment group. These include treatment emergent adverse events, serious adverse events, drug-related adverse events, and adverse events leading to withdrawal from treatment. For the calculation of the number and percentage of subjects, if a subject had multiple adverse events of the same SOC and PT, only one event will be counted.

Among treatment emergent adverse events, the incidence (number and percentage of subjects) of various treatment emergent adverse events and drug-related adverse events will be calculated by system organ class (SOC), preferred term (PT), and severity (mild, moderate, severe). If a subject had multiple adverse events with the same preferred term, such event is counted only once within such preferred term, and the event with the highest severity is counted.

System organ class (SOC) and/or preferred term (PT) will be presented in a descending order of incidence in the ARNI treatment group and incidence in the ACEI/ARB treatment group.

All adverse events, serious adverse events, and adverse events leading to withdrawal from treatment will be listed separately. A detailed list describing details of subject deaths will be provided.

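### SAP 4.2.2 allocates adverse events to ACEI/ARB or ARNI by when they occur and does not carry its own worsening rule across the switch, as Protocol 12.5.3 requires

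*SAP*

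**What the plan says.** Protocol 12.5.3 (Safety endpoints) says which events count for a specific treatment period. They are events with onset after that period starts, and also earlier events "which were present prior to the start of the treatment period but increased in severity, changed from being not suspected to being suspected" of a relationship to study drug, or that became SAEs once the period had begun.

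SAP 4.2.2 has two layers:

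- **General definition.** A TEAE is an event between the first dose of study drug and 30 days after the last study treatment. The definition adds "events occurring before the start of the treatment period and meeting any of the following three changes": worsening, a change to suspected, or becoming an SAE. Worsening is then explained by comparison with the worst grade before the first administration of the investigational drug. TEAEs are to be counted by treatment period.
- **Allocation to columns.** For the control period, "TEAEs in the ACEI/ARB treatment group refers to the adverse events that occur after the" subject's "first ACEI/ARB administration and before ARNI administration". A patient who never takes ARNI is followed to 30 days after the last ACEI/ARB dose. For the other period, "TEAEs in the ARNI treatment group refer to adverse events that occur from the" first ARNI dose to 30 days after the last one. Neither sentence mentions the three changes.

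SAP 7.5.2 tabulates by severity. If a patient has several events with one preferred term, "such event is counted only once within such preferred term, and the event with the highest severity is counted".

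**The concern.** The design is a fixed sequence: six months of ACEI/ARB, then six months of ARNI, in the same patients. An event can therefore start in the first period, still be open at the switch, and get worse or become serious in the second. The protocol has a rule for this case, and the SAP sentences that fill the two columns leave it out.

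Safety has no formal inference in this trial, so the descriptive columns are the safety comparison. The interim analysis is also meant to look for a high incidence of safety events (Protocol 4.5). If an event aggravated after the switch stays only in the ACEI/ARB column, the ARNI column is too low. The order of drugs is the same for everyone, so the opposite misallocation cannot offset it.

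**Working it through.** No arithmetic applies, because the documents attach no figure to this rule. The check is to follow one event through the text.

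1. **Does an event that starts on ACEI/ARB need the three changes to be a TEAE?** No. It already qualifies by starting after the first dose of study drug. The three changes then have no work to do in making it a TEAE, and the only text that picks a column is the pair of time windows.

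2. **Does the worsening clause operate at the switch?** That depends on what the investigational drug is, and the SAP does not say.
   - *First study drug (ACEI/ARB).* The pre-treatment definition in SAP 4.2.2 uses the same term to end the interval that begins at consent. The AE date imputation in SAP 7.2.1 also classifies against it, with no separate rule for the first ARNI dose. On this reading, an event that began on ACEI/ARB was not present before the reference dose, so the worsening clause cannot operate at the switch.
   - *ARNI.* The Protocol glossary defines the investigational drug as the one under test, and Protocol Table 6-1 lists ACEI and ARB as control drugs. On this reading the clause does operate at the switch.

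3. **Trace one event.** Suppose a mild event starts between the Month 3 and Month 6 visits, is kept as one record, and becomes severe between the Month 7 and Month 9 visits.

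| Rule | ACEI/ARB column | ARNI column |
|---|---|---|
| Protocol 12.5.3 | counted (onset) | counted (worsened in that period) |
| SAP 4.2.2 allocation sentences, taken literally | counted | not counted |
| SAP 4.2.2, general definition applied per period | counted | counted |
| Either document, if worsening is entered as a new record | counted | counted (new onset on ARNI) |

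   Two programmers could produce different tables from the same SAP.

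4. **Will worsening be a new record?** The documents do not settle this. Protocol 10.1.1 has an AE followed to resolution with severity reassessed at each visit. Protocol 10.1.3 treats progression and recurrence of an SAE as follow-up to the original report, but wants an SAE at a different time interval reported separately. Neither section requires a new record with a new start date when a grade changes.

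5. **Which severity appears under ACEI/ARB?** SAP 7.5.2 chooses among several events with the same preferred term. It is silent on one record whose grade changes, and it does not cut severity off at the first ARNI dose.

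6. **Size.** Neither document gives a number or an expected rate of events that span the switch.

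**The case against.** The strongest reply is that the rule is already in the SAP. The three changes appear in 4.2.2 just before the allocation sentences, they follow the protocol closely, and the section says TEAEs are counted by period. A careful programmer could apply them to each period. The reference-dose problem touches only worsening, because the changes to suspected and to serious have no such anchor. One fair reading of the investigational drug makes the first ARNI dose the reference already. Another paragraph of Protocol 12.5.3 also limits AE tables to events with a start date in the on-treatment period.

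Much of this stands. A reader might infer that the SAP counts by onset alone and that an event begun on ACEI/ARB can never reach the ARNI column. The text does not support that: the general definition can be read to include such events, and a separate record opened on ARNI falls in the ARNI window in any case. A reader might also infer that a severity reached on ARNI will be shown under ACEI/ARB. That depends on CRF practice that the documents do not describe.

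What does not stand is that the general definition settles the column. It decides what is a TEAE; the next sentences decide where it goes, and they depart from the protocol. The protocol's start-date sentence does not split the on-treatment period by drug, whereas its period-specific paragraph does.

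Other outputs soften the effect: AE and SAE listings, a separate summary of deaths, and laboratory and vital-sign summaries, with Visit 4 as the ARNI baseline. They do not replace the period-specific incidence tables.

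**Conclusion.** The SAP's allocation sentences, as written, depart from Protocol 12.5.3. Taken literally, they omit from the ARNI column an event held in one record that began on ACEI/ARB and worsened, became suspected or became serious after the switch. The direction is fixed by the treatment order: any such misallocation understates ARNI events.

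The amount cannot be sized. Applying an assumed percentage to the planned 175 evaluable patients would give a shift in incidence, but the percentage would have no source in the documents and no such figure should be attached.

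The conclusion rests on two assumptions: that the allocation sentences are programmed literally, and that at least some changes after the switch are kept in the original AE record. If either fails, the tables may already agree with the protocol. The primary efficacy analysis is unaffected. The point is still worth correcting, because it concerns the safety comparison between the two drugs and is cheap to close.

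**What to change.** In SAP 4.2.2:

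- Add to the ARNI sentence that an AE present before the first ARNI dose which increases in severity, becomes suspected or becomes an SAE on or after that dose is an ARNI TEAE, at its post-switch severity, causality and seriousness. The first ARNI dose is the reference for an increase in severity in that period.
- Add the matching clause to the ACEI/ARB sentence, with the first ACEI/ARB dose as the reference.
- Define the treatment period and the investigational drug for each period.

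In SAP 7.5.2, state that ACEI/ARB tables use the event's status before the first ARNI dose where the CRF dates the change. Where it does not, note the limitation with the listing.

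The cost is a few sentences of SAP text, the corresponding programming, and a check of whether the CRF dates changes in grade, causality and seriousness. The counting rule in the protocol needs no change, since this restores it.
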